6.3. Reporting of Serious Adverse Events (SAE)

An adverse event that meets one of the seriousness criteria (6.1.3) is classified as a SAE. SAEs are reported on the SAE eCRF which is emailed to the Transfusion Research Unit at Monash University ([contact]). A copy of the report will be forwarded to the site Pharmacy.

At a minimum, the following attributes must be assigned at the initial report:

- Adverse event term
- Seriousness criterion
- Date of onset and outcome

- Severity of the event (CTCAE Grade)
- Assessment of relatedness to the assigned intervention (Section 6.2 Causality)
- Assessment of expectedness for the assigned trial intervention

Subsequent reports must contain:

- A detailed description of the event
- Relevant laboratory findings and hospital reports
- Other concomitant drugs or devices

All SAEs will be followed until resolution. The investigator will be asked to provide interim and follow-up reports, as necessary, if the SAE has not resolved at the time of initial report.

6.3.1. Adverse Events that require expedited reporting (within 24 hours)

Any SAEs or SARs or unexpected (but not serious) adverse reactions (UARs) must be reported to Monash University within 24 hours of the investigator becoming aware of the event, unless these have been specifically excluded from expedited reporting. These are SAEs that are associated with the participant's underlying disease, and will not impact on the scientific interpretation of the results of the trial.

Due to the seriousness of the underlying diseases from which the participants in this trial are suffering, the following situations that fulfil the definition of an SAE are excluded from expedited notification, but should be recorded on the SAE form and reported within 5 working days:

- Hospitalisation for pre-existing conditions that, in the investigator's opinion, have not been exacerbated by trial intervention
- Any other serious event related to the underlying disease or other medications used to treat the disease. Serious infections are not excluded from expedited notification.

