3.2. OUTCOMES

3.2.1. Primary outcome

Event-free survival (EFS), defined as time from randomisation (or, in domains with a single treatment arm, time from registration) until occurrence of a Grade 3 or higher infection (as defined by CTCAE Version 5), or death from any cause.

This is the primary outcome for trial results for each domain, unless otherwise specified in the Domain Specific Appendix.

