6.1.2. Adverse Reaction (AR)

Any untoward and unintended response to an investigational medicinal product related to any dose administered. All adverse events judged by either the reporting investigator or the sponsor as having a reasonable possibility of a causal relationship to an investigational medicinal product would qualify as adverse reactions. A causal relationship between the trial treatment (or medication error, misuse/abuse of medicinal product) and an adverse event occurs where there is at least a reasonable possibility that the trial treatment caused the event, i.e. the relationship cannot be ruled out.

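### The second exclusion from 24-hour reporting in Protocol 6.3.1 has no test of relation to trial treatment, so a non-infectious suspected serious reaction can take the 5-working-day route

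*Protocol*

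**What the plan says.** Section 6.3.1 sets the general rule: "Any SAEs or SARs or unexpected (but not serious) adverse reactions (UARs) must be reported to Monash University within 24 hours". The clock starts when the site investigator learns of the event, and the rule holds "unless these have been specifically excluded from expedited reporting". A lead-in describes the excluded events as SAEs tied to the malignancy, and says of them that they "will not impact on the scientific interpretation of the results of the trial". Two exclusions follow, each with a limit of 5 working days for the report:

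- The first is "Hospitalisation for pre-existing conditions that, in the investigator's opinion, have not been exacerbated by trial intervention". Here the investigator's view of trial treatment decides.
- The second is "Any other serious event related to the underlying disease or other medications used to treat the disease". Here it does not, although a closing sentence returns serious infections to the 24-hour route.

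No other event type is returned.

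Section 6.1.2 treats an event as an adverse reaction when there is "at least a reasonable possibility that the trial treatment caused the event, i.e. the relationship cannot be ruled out". Section 6.2.1 has five causality grades. The middle one, possibly related, is for events with a temporal association where another cause is nonetheless likely. Section 6.3 requires a relatedness assessment in the initial SAE report. Section 6.3.2 requires every death to go on the SAE form and the eCRFs, with no time limit. Section 3.2.1 counts as a primary-outcome event a Grade 3 or higher infection "or death from any cause".

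**The concern.** The two exclusions are drafted unequally. The narrower one asks whether trial treatment played a part. The broader one asks only whether the disease or its other drugs did. In this population the two explanations often coexist. A thrombosis in someone receiving both immunoglobulin and anticancer drugs is an example. Section 2.1.1.2 itself says that immunoglobulin side-effects can occasionally be serious, and cites a study of thromboembolic events after intravenous immunoglobulin in patients with haematological malignancy.

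What is at stake is the time at which the sponsor first hears of a suspected serious reaction. The sponsor may judge causality itself (6.1.2), assesses expectedness for all SAEs (6.2.1) and reports SUSARs (6.3.4). None of this can begin before notification. Treatment is open-label by default (4.5.4), so the person choosing between explanations, and so between reporting routes, usually knows the assigned arm.

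**Working it through.** The protocol gives no figure to reproduce. The check is to apply the wording of 6.1.2, 6.2.1, 6.3.1 and 6.3.2 to a set of cases and read off the time limit.

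| Case | 24-hour rule met? | Exclusion met? | Limit as written |
|---|---|---|---|
| A. Non-serious unexpected reaction | Yes | No; exclusions cover SAEs only | 24 hours |
| B. Serious infection | Yes | No; returned to the 24-hour route | 24 hours |
| C. Hospitalisation for a pre-existing condition not linked to the malignancy or its drugs, thought to be worsened by trial treatment | Yes | No; fails the test in the first exclusion | 24 hours |
| D. Non-infectious SAE due to the disease or its drugs, graded unrelated to trial treatment | Yes | Yes, second exclusion | 5 working days |
| E. The same SAE, graded possibly related to trial treatment | Yes, as SAE and SAR | Yes, second exclusion | 5 working days |
| F. Non-infectious death attributed to the malignancy | Yes | Yes by the second exclusion; doubtful by the lead-in | Unclear |

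**Case E, step by step.**
1. Graded possibly related, the event has a link to trial treatment that cannot be ruled out, so by 6.1.2 it is an adverse reaction. Being serious, it is a SAR.
2. The disease or its drugs are the likely cause, so it is also related to them and fits the second exclusion.
3. The exception in the general rule follows the whole list of reportable events, SARs included. A specific exclusion therefore displaces the 24-hour limit.
4. Relatedness is recorded on the initial report, but the second exclusion does not use it to choose the route.

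**A and E compared.** A reaction that is unexpected but not serious always goes within 24 hours. A serious suspected reaction with two plausible causes may wait 5 working days. That reverses the usual priority and is unlikely to be intended.

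**Case F.** The second exclusion admits the death, because it is a serious event related to the disease. The lead-in limits exclusions to events that do not affect interpretation, yet all-cause death is a component of the primary outcome. Section 6.3.2 does not settle the matter.

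**Size of the delay.** Across one weekend, 5 working days + 2 weekend days = 7 calendar days, against 1 day. Both are upper limits, not expected delays. The protocol does not say when the 5 days start; I assume from awareness, as for the 24 hours.

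**The case against.** The other side has four textual arguments.

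- The lead-in can be read as a limiting condition, not only a justification, and a suspected reaction or a death arguably fails it.
- The second exclusion speaks of other medications, which suggests attribution away from trial treatment. It resembles the unrelated grade in 6.2.1.
- The general rule names SAEs and SARs separately, but the exclusions refer only to events meeting the SAE definition, so a strict reader might keep SARs at 24 hours.
- Because even non-serious unexpected reactions go within 24 hours, the coherent reading is that the second exclusion covers only events attributed elsewhere.

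These arguments show what was probably meant. They do not supply the missing condition. Impact on interpretation is not a causality test. Relation to another drug does not rule out relation to the trial drug. Every SAR also meets the SAE definition. A site following the words could take either route.

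Several stronger inferences are tempting, and the documents do not support them:

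- *Late notice of deaths damages the primary analysis.* Event-free survival depends on the date of the event, not on when the sponsor is told, and deaths go on the eCRFs as well.
- *Death is half the endpoint.* It is one of two components, and no split of events is given.
- *Urgent safety measures are held up.* Section 6.1.6 lets the investigator act at once and has its own 24-hour reporting rule. Sections 6.3.3 and 6.3.5.2 add reporting to the institution, the transfusion service and others.
- *Most serious reactions would be absorbed.* Nothing gives the share with dual attribution. The infection-death percentages in 2.1.1.1 are background on CLL and early myeloma, not forecasts for this trial.

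Domain and region appendices are not shown and could add reporting rules. The core text, which serves every domain, would still need to be consistent.

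**Conclusion.** The gap is real and should be corrected, but it is limited. As written, a non-infectious serious event that is possibly related to trial treatment, with the disease or its drugs as the likelier cause, may be reported within 5 working days and not 24 hours. The consequence is later sponsor assessment of causality, expectedness and SUSAR status. The event is still reported, with a relatedness grade. How often this would happen cannot be estimated from the protocol.

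The treatment of non-infectious deaths is a separate ambiguity: the lead-in and the second exclusion point in different directions. It is a matter of consistency, not of bias in the results.

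The conclusion assumes that a possibly related grade amounts to a relationship that cannot be ruled out. Section 6.1.2 implies this, but no table in the protocol maps grades to adverse reactions. It also assumes that no appendix overrides 6.3.1.

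**What to change.** Three changes to 6.3.1:

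1. Add to the second exclusion a condition that, in the investigator's opinion, there is no reasonable possibility that the trial intervention caused the event, so that it is not a SAR. The test must rest on the investigator alone, because the site chooses the route before the sponsor knows of the event.
2. State that where an event meets both the 24-hour rule and an exclusion, the 24-hour rule prevails.
3. Reconcile the lead-in with all-cause death as a primary-outcome event, by saying whether non-infectious deaths fall under the exclusion, and cross-refer from 6.3.2.

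The cost is a short protocol amendment and a line in site training. The downside is a modest increase in 24-hour reports, made on an SAE form that is already required for the same events.

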6.3.2. Death

All deaths occurring on trial must be reported as an outcome on the SAE form and on the eCRFs. For all deaths, available autopsy reports (or death certificate if available) should be sent with the notification.

NB: Death is the outcome of a SAE; it cannot be the AE term unless no other information is available.

6.3.3. Investigator responsibilities

All SAEs must be assessed by, and reports signed, by an Investigator.

It will be left to the investigator's clinical judgment whether or not an adverse reaction is of sufficient severity to require that the participants should be discontinued from the treatment. A participant may also voluntarily withdraw from treatment due to what they perceive as an intolerable adverse event. If either of these occurs, it must be made clear if the participant is being withdrawn from the trial or just the trial intervention.

The Investigator is responsible for reporting SUSARs arising at their site, Significant Safety Issues (SSIs) and Urgent Safety Measures (USMs) to their Institution.

6.3.4. Sponsor responsibilities

Monash University is the trial sponsor and has ultimate responsibility for the ongoing safety evaluation of the trial. Where required, Monash University is responsible for the reporting of Australian SUSARs to the Therapeutic Goods Administration (TGA), annual safety reports to the HREC, and Significant Safety Issues (SSIs) and Urgent Safety Measures (USMs) to the TGA, HREC and Investigators. Reporting requirements in other regions is outlined in the relevant RSA.

All adverse events will be reviewed by the Chief Investigator (or a medically qualified delegate). The Chief Investigator will provide listings of all events for review by the DSMC and reports of AEs will be forwarded to the DSMC for review as often as required by the DSMC.

6.3.5. Statutory reporting

6.3.5.1. Reporting to the Therapeutic Goods Administration

For trials conducted under the Clinical Trials Notification (CTN) scheme Sponsors must report AEs that meet TGA criteria.

6.3.5.2. Reporting of suspected reactions to trial treatments

Adverse events or suspected transfusion reactions to Ig should be reported to the site's transfusion service in accordance with hospital requirements, and to the product sponsor, national blood service and/or haemovigilance programs in line with national guidelines and reporting criteria. UARs to trial antibiotics should also be reported in accordance with site and national pharmacovigilance program requirements.

7. ETHICAL CONSIDERATIONS

7.1. Compliance

This trial is to be performed in accordance with the ethical principles of the Declaration of Helsinki (October 2013), the Integrated Addendum to ICH E6 (R1): guideline for Good Clinical Practice ICH E6 (R2) (November 2016) annotated with Therapeutic Goods Administration comments, and the NHMRC National Statement on Ethical Conduct in Human Research 2007 (Updated 2018). Sites in jurisdictions other than Australia are responsible for ensuring that their safety and ethical reports also comply with their region, as documented in the RSA.

7.2. Ethical conduct of the trial

In order to safeguard the rights, safety and well-being of participants, this protocol will be submitted to a Human Research and Ethics Committee (HREC) constituted according to the local requirements. Approval of the protocol, template Patient Information and Consent Form (PICF), participant education and recruitment materials, and other relevant trial documents will be obtained prior to the start of the trial.

The Sponsor will ensure that all conditions for approval of the trial are met and that subsequent amendments are notified to, and approved by the HREC prior to implementation.

The Sponsor will produce progress and safety reports for the HREC in accordance with their requirements. The Sponsor will keep an up to date record of all applicable documentation and correspondence with the HREC.

It is the responsibility of the Principal Investigator at each participating site to ensure that the protocol, site-specific PICF, participant education and recruitment materials, and other requested documents, as well as all subsequent amendments, are notified to the applicable local governance office. Approval must be obtained from the Sponsor, ethics committee and local governance office for the platform, and any domains in which the site plan to participate, prior to participation in those domains.

7.3. Protocol amendments

Any modifications to the protocol which may impact on the conduct of the study, potential benefit of the patient or may affect patient safety, including changes of study objectives, study design, patient population, sample sizes, study procedures, or significant administrative aspects will require a formal amendment to the protocol. Such amendment will be agreed upon by the ITSC, and approved by the HREC prior to implementation and notified to the health authorities in accordance with local regulations.

Administrative changes of the protocol are minor corrections and/or clarifications that have no effect on the way the study is to be conducted. These administrative changes will be agreed upon by the TMG, and will be documented in a memorandum. The HREC may be notified of administrative changes at the discretion of the TMG.

7.4. Consent

Informed consent will be sought by the Principal Investigator or appropriately trained delegates. The method of obtaining and documenting the informed consent and the contents of the consent will comply with ICH GCP and all applicable regulatory requirements. Additionally, where required per national or local guidelines, local consent for a specific study intervention (e.g. immunoglobulin replacement) will be taken by the investigator or a delegate, and stored in institutional records - this is the responsibility of the Principal Investigator.

The participant will be provided with a Patient Information and Consent Form (PICF) about the trial and written consent sought once the participant has been given the opportunity to discuss the trial with the PI or delegate.

Participants will not take part in the trial unless fully-informed consent has been obtained. No trial-specific procedures may be conducted prior to informed consent. However, any tests or procedures conducted as part of participants' routine clinical care (e.g., non-trial-specific blood tests etc.), may be utilised for baseline purposes, provided those procedures were conducted within the designated baseline period, and according to protocol requirements.

Participants who are already enrolled in the platform and are rotating from one domain to the next will not need to be re-consented to the platform at the time of rotation, but they will need to be consented to the subsequent domain. Per local Investigator discretion and local site procedures, the participant may be reconsented to the platform if a considerable amount of time has lapsed since the original platform consent was obtained.

7.5. Patient confidentiality and access to data

CRFs, clinical notes and administrative documentation should be kept in a secure location (for example, locked filing cabinets in a room with restricted access) and held for a minimum of 15 years after the end of the trial, depending on regional requirements. During this period, all data should be accessible to the competent authorities and the Sponsor with suitable notice.

All laboratory specimens, reports, data collection, process, and administrative forms will be identified by a coded ID [*identification*] number only to maintain participant confidentiality.

Following completion of analysis, the trial database will be archived for at least 15 years in accordance with Monash University policy.

8. INDEMNITY AND FINANCE

Indemnity arrangements will be described in the clinical trial research agreement (CTRA) which will be in place with each participating site.

Initial funding for this trial has been provided by the National Health and Medical Research Council (NHMRC) and Medical Research Future Fund with clinical trial management support from the TRU, Monash University, Australia. Details of payments to sites to cover the research costs will be provided in the CTRA.

Declaration of interests

None of the individuals named in this protocol have any competing interests to declare.

9. PUBLICATION

9.1. Dissemination

The results from different centres will be analysed together and published as soon as possible. Individual clinicians must not publish data concerning their patients that are directly relevant to questions posed by the trial until the ITSC has published its report. The ITSC will form the basis of the Writing Committee and will advise on the nature of publications.

9.2. Authorship

Authorship of final papers will consist of persons who have made a significant contribution to design, management and/or recruitment of the clinical trial and in accordance with the trial authorship policy. Authorship of the publication and significant contribution shall be considered by the Trial Writing Committee.

9.3. Timing

No data may be made public before publication and never without agreement from the CIs.

9.4. Acknowledgements

The Study Funder, Sponsor and the relevant Trial Committees must be acknowledged on all publications as well as the role of the Clinical Trials Unit in providing support for and running this study. All contributing PIs must be listed.

